7.3.5.3 Healthcare Utilization Characteristics

- **Provider specialty**—A count of unique days with a non-inpatient claim for treatment by provider specialty category (primary care physician [including general/family practice, internal medicine], pulmonology and rheumatology) will be reported.
- **Medication use**—ILD medication use will be captured at the class level, including administrations and prescription fills. The number of prescriptions fills within each class will also be calculated. Treatment categories will include corticosteroids (methylprednisone, prednisone, prednisolone), biologics, (abatacept, denosumab, etanercept, tocilizumab, infliximab, rituximab), calcineurin inhibitors (cyclosporine, tacrolimus), and other immunosuppressants (mycophenolate mofetil, hydroxychloroquine, leflunomide, methotrexate, sulfasalazine, chloroquine phosphate).
- **All-cause HCRU**—HCRU will be calculated for ambulatory visits (physician office and hospital outpatient), emergency department (ER) visits, inpatient admissions, and pharmacy fills.
- **All-cause health care costs**—Health care costs will be presented as standardized costs. Total costs will be calculated and presented in categories of pharmacy costs and medical costs (outpatient, inpatient, professional services). Costs will be adjusted using the annual medical care component of the Consumer Price Index (CPI) to reflect inflation between the date of the claim and the most recent year for which the annual CPI is available.

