date (i.e., similar to the matched oxygen therapy patient in time from the fibrosing ILD diagnosis date to the index date, and during the same continuous enrollment period as the fibrosing ILD diagnosis date).

NOTE: Following review of results from Aim 1, the study team will determine whether continuous enrollment criteria for Aim 2 and Further Aim requires revision.

Variables:	
Aim 1
 
Outcomes: time to initiation of oxygen therapy; time to sustained oxygen therapy use; sustained oxygen therapy use within the first 12 months of follow-up
 
Baseline covariates: demographic characteristics (age, sex, race/ethnicity, geographic region, insurance type, index year), clinical characteristics (underlying ILD type; respiratory diseases; other clinical characteristics; Quan-Charlson comorbidity score; Agency for Health Research and Quality [AHRQ] comorbid conditions; smoking; pulmonary rehabilitation) healthcare utilization characteristics (provider specialty; medication use; all-cause HCRU; all-cause health care costs)
 
Stratification: IPF vs non-IPF ILD
 
Aim 2 [REDACTED]
 
Exposure: oxygen therapy vs no oxygen therapy
 
Primary Outcomes: Time to disease progression; time to all-cause mortality; time to hypoxemia, time to acute exacerbations, counts of acute exacerbations
 
[REDACTED]
 
Baseline covariates: demographic characteristics (index year, age, sex, race/ethnicity, geographic region, insurance type), clinical characteristics (underlying ILD type; respiratory diseases; other clinical characteristics; Quan-Charlson comorbidity score; AHRQ comorbid conditions; smoking; pulmonary rehabilitation) healthcare utilization characteristics (provider specialty; medication use; all-cause HCRU; all-cause health care costs)

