5. RATIONALE AND BACKGROUND

Interstitial lung disease (ILD) is a broad term that describes more than 200 diverse lung disorders, including idiopathic pulmonary fibrosis (IPF), autoimmune ILD, hypersensitivity pneumonitis (HP), and sarcoidosis.¹ Typical symptoms of ILD include cough and dyspnea, as well as decreased lung capacity², which leads to exercise intolerance and hypoxemia.

The major goal of therapy in ILD patients is to slow disease progression as well as improve the associated dyspnea, exercise capacity, and health-related quality of life.³ Approved treatment options for fibrosing ILD comprise antifibrotic treatments including nintedanib and pirfenidone, which slow the rate of decline in forced vital capacity (FVC). Other commonly prescribed treatment options are corticosteroids, immunosuppressants, opioids, and lung transplantation.⁴ Despite advances in pharmacotherapy, many patients continue with disease progression. Oxygen therapy is commonly administered to reduce breathlessness and increase physical capacity by improving gas exchange.⁵

Supplemental oxygen (O₂) is commonly prescribed in clinical practice for patients with fibrotic ILD; however, robust evidence to support its long-term use is lacking. Recommendations for long-term oxygen therapy (LTOT) for resting hypoxemia in ILD are largely extrapolated from trials conducted in chronic obstructive pulmonary disease (COPD), where a survival benefit is well established.^{6,7} The American Association for Respiratory Care guideline recommends the use of oxygen therapy to maintain the oxygen saturation (SpO₂) range of 94–98% for most hospitalized patients.⁸ Despite its frequent use, there is a paucity of studies evaluating the incidence, prevalence, and impact of LTOT on outcomes such as disease progression or mortality in ILD. This study will help fill in the gaps in increasing the understanding of the use of oxygen therapy among fibrosing ILD patients and assess whether the use of oxygen leads to better or worse outcomes.

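### The ILD medication covariate lists denosumab, a bone-loss antibody, among the ILD biologics and lists no class for opioids or antifibrotics, which the protocol's own rationale names.

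*Combined protocol and SAP*

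**What the plan says.** Section 7.3.5.3 of the combined protocol and SAP defines the variable: "ILD medication use will be captured at the class level, including administrations and prescription fills". It adds a quantity variable: "The number of prescriptions fills within each class will also be calculated". It then lists four classes:

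- corticosteroids: "Treatment categories will include corticosteroids (methylprednisone, prednisone, prednisolone"
- biologics: "biologics, (abatacept, denosumab, etanercept, tocilizumab, infliximab, rituximab"
- calcineurin inhibitors and other immunosuppressants: "calcineurin inhibitors (cyclosporine, tacrolimus), and other immunosuppressants (mycophenolate mofetil, hydroxychloroquine, leflunomide, methotrexate, sulfasalazine, chloroquine phosphate"

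The Abstract puts this variable among the baseline covariates for both aims: "healthcare utilization characteristics (provider specialty; medication use; all-cause HCRU; all-cause health care costs". Section 7.6.1.3 names medication use as a candidate covariate in the Aim 1 Cox model for oxygen initiation. It plans to report a hazard ratio, 95% CI and p-value for every covariate in that model.

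Section 5 sets out the treatments the authors regard as relevant. On approved treatment: "Approved treatment options for fibrosing ILD comprise antifibrotic treatments including nintedanib and pirfenidone". On the rest: "Other commonly prescribed treatment options are corticosteroids, immunosuppressants, opioids, and lung transplantation".

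**The concern.** There are two problems of content.

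First, denosumab is not an immune or ILD treatment; the other five listed biologics are immune-directed. Because the variable is built at class level, a patient treated only for osteoporosis is coded as receiving ILD biologic therapy and cannot later be separated. Any biologics hazard ratio in Aim 1 would then describe a mixture. In Aim 2, balancing or adjusting on that class would balance the mixture and not the immune therapy.

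Second, the class list has not been reconciled with the rationale. Antifibrotics are the only treatments the rationale calls approved for fibrosing ILD. Opioid use for breathlessness is a plausible marker of advanced disease, so it could predict both oxygen initiation and death. The visible covariate lists for the two aims do not name FVC, DLCO or SpO2, so adjustment for severity rests largely on proxies, and a missing proxy matters more than it otherwise would.

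**Working it through.** The plan states no figure that could be reproduced here. The check sets the treatments named in Section 5 against the covariates listed in Sections 7.3.5.2 and 7.3.5.3.

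| Treatment named in the rationale | Listed covariate |
|---|---|
| Antifibrotics (nintedanib, pirfenidone) | none |
| Corticosteroids | class in 7.3.5.3 |
| Immunosuppressants | classes in 7.3.5.3 |
| Opioids | none |
| Lung transplantation | indicator in 7.3.5.2 |

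Two of the five have no listed covariate. In the other direction, denosumab is listed in 7.3.5.3, and no part of the document explains why.

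**Count variable.** The use indicator draws on administrations and fills; the count draws on fills only. A patient whose only record is an administration is therefore coded as a user with a count of 0. Section 7.4 says the dataset holds medications both prescribed and administered, so a combined count is feasible.

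**Illustration 1: dilution of the biologics factor.** All inputs are assumptions. Let b be the share of patients on an immune biologic (3% to 5%) and d the share on denosumab (2% to 4%). Assume no overlap, no effect of denosumab use on the hazard, and a true HR of 1.5 for immune biologics.

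- Misclassified share of the class = d / (b + d). Low: 0.02 / (0.05 + 0.02) = 29%. High: 0.04 / (0.03 + 0.04) = 57%.
- Class HR ≈ 1 + (1.5 − 1) × (1 − share). Low share: 1 + 0.5 × 0.71 = 1.36. High share: 1 + 0.5 × 0.43 = 1.21.

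**Illustration 2: opioids as an unmeasured confounder of oxygen and mortality.** All inputs are assumptions. Let p1 and p0 be pre-index opioid use in the oxygen and comparison cohorts, and R the mortality ratio for opioid users. With a true oxygen HR of 1, the apparent HR ≈ [1 + p1(R − 1)] / [1 + p0(R − 1)].

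- p1 = 30%, p0 = 15%, R = 2: 1.30 / 1.15 = 1.13
- p1 = 25%, p0 = 15%, R = 1.5: 1.125 / 1.075 = 1.05
- p1 = 40%, p0 = 15%, R = 2.5: 1.60 / 1.225 = 1.31

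This second calculation treats opioids as the only confounder and lets the whole imbalance survive matching. No comparable calculation was made for antifibrotics.

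**The case against.** The case on the other side has five parts.

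1. *The class list may not be closed.* The wording says which categories will be included, which need not mean only those. The drug code lists in Annex 4 are not reproduced. This stands: absence from the listed classes is shown, absence from the analysis data is not. It does not help with denosumab, which is expressly listed.

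2. *The Aim 2 matching covariates cannot be read.* Section 7.2.3 refers to Section 7.6.2.2, which is not in the public text. A reader might infer that opioid use is left unadjusted in Aim 2 and that oxygen will therefore look harmful. The documents do not establish that. They show only that the Aim 2 baseline covariates include medication use and that its listed classes contain no opioids.

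3. *Other severity proxies are already listed.* They include acute respiratory failure, pulmonary hypertension, lung cancer and heart failure (7.3.5.2), utilization and costs (7.3.5.3), and hypoxemia, which Table 1 marks for the pre-index baseline. Section 7.8 also concedes residual confounding. This stands as a limit on size: correlated covariates would probably absorb part of the 1.13. It is no reason to omit a measurable proxy that the rationale names.

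4. *Infused drugs are not missed.* A reader might infer from the fill count that drugs given by infusion go unrecorded. The definition contradicts this, because administrations count as use. Only the supplementary count is limited to fills, and no visible section puts that count in a model.

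5. *Harm from denosumab is assumed.* The prevalences are not in the documents. The dilution formula gives denosumab users a hazard ratio of 1, which is doubtful if they tend to be older and steroid-treated. Medication use is also only one candidate covariate. All of this limits the numbers. The class would remain a mixture whatever the prevalences.

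**Conclusion.** The point holds in limited form. The biologics class contains a drug that does not belong with the others, and any hazard ratio reported for it would be hard to interpret. On the visible text, opioids and antifibrotics have no medication class although the rationale names both. The fill-only count is minor.

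The size of any bias cannot be derived from the documents. The ranges 1.21 to 1.36 (dilution of a true 1.5) and 1.05 to 1.31 (apparent oxygen effect under the null) show direction and possible scale under assumed inputs; they are not forecasts. The conclusion rests on general pharmacology for what denosumab treats, and on the unseen code lists not already containing the missing classes. The definition should be corrected because the correction is cheap and the affected covariate serves both aims.

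**What to change.** In Section 7.3.5.3 and the drug code list:

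- Remove denosumab from the biologics class, or state the reason for listing it.
- Add an opioid class and an antifibrotic class (nintedanib, pirfenidone) to baseline medication use, so that both are candidates for the Aim 1 Cox model and belong to the Aim 2 baseline covariates. If the code lists already contain them, name them in 7.3.5.3.
- If the per-class count is to be reported or modelled, count distinct administration and fill dates.

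This is a code-list and covariate edit on claims and EHR data already held. Section 7.7 makes the client responsible for checking code lists before approving the final protocol, and warns that changes after approval bring additional time and fees.

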7.4 DATA SOURCES

Figure 3. Optum Data Ecosystem

Optum's Clinical EHR Database aggregates extensive clinical encounter data from a network of 140,000+ providers at more than 700 hospitals and 7,000+ clinics. The Clinical EHR Database currently has more than 104 million unique patients across the United States, with an average of 45 months of observed data per patient.

The Clinical EHR Database is robust, longitudinally linked, compliant with the Health Information Portability and Accountability Act of 1996 (HIPAA), and statistically de-identified. Data elements include demographics; medications prescribed and administered; immunizations; allergies; lab results (including microbiology); vital signs and other observable measurements; clinical and inpatient stay administrative data; and coded diagnoses and procedures.

Optum's Clinical EHR Database can deliver a longitudinal record that covers a comprehensive spectrum of patient health, medical information, and treatment decisions.

Optum Market Clarity dataset

The Optum Market Clarity dataset includes de-identified, deterministically linked claims data integrated with Optum's Clinical EHR data. It is fully HIPAA-compliant and statistician-certified. Clinical data are combined with adjudicated medical and pharmacy claims from both Optum-affiliated and non-affiliated payers. The Market Clarity dataset links EHR data with historical, linked administrative claim data, pharmacy claims, physician claims, facility claims (with clinical information), medications prescribed and administered, diagnoses, procedures, and information derived from clinical notes using NLP. For this study, the subset of individuals with health plan enrollment data available will be used. Insurance coverage will include commercial, Medicaid, and Medicare.

Figure 4. Market Clarity Data**7.5 STUDY SIZE**

Using data for Market Clarity integrated claims and clinical EHR data from 01 Jan 2016 - 31 May 2022, 1,179,017 patients with fibrosing-ILD were identified. Among them, 34,299 adult patients had at least one claim for oxygen therapy with 6 months of continuous enrollment in claims and 6 months of continuous activity in EHR.

These counts are for informational purposes only and may not reflect the final sample size. Application of other inclusion and exclusion criteria required for this study or other factors may reduce the sample size.

Table 3. Feasibility Counts from Market Clarity

Criteria	N
Commercial and Medicare Advantage health plan members with ≥ 1 medical claim or EHR diagnosis for fibrosing interstitial lung disease (ILD) during 01 JAN 2016 and 31 MAY 2022 (study period). First diagnosis is index date.	1,179,017
Patients with at least one evidence for oxygen therapy anytime during the post-index period (12 months)	214,725
Patients aged ≥ 18 years as of the index date	212,466
Patients with at least 6 months of pre-index continuous enrollment and EHR clinical activity	80,151
Patients with at least 6 months of post-index continuous enrollment and EHR clinical activity	34,299

7.6 DATA ANALYSIS

All analysis will be conducted using SAS statistical software (version 9.4 or higher, [REDACTED] and Microsoft Excel.

7.6.1 Aim 1 Analysis

7.6.1.1 Descriptive Analysis

All variables will be analyzed descriptively, and results will be stratified by cohort (IPF vs non-IPF ILD). Numbers and percentages will be provided for categorical variables. Means, medians, and standard deviations, will be provided for continuous variables. Appropriate statistical comparisons will be conducted based on the distribution of the measure.

7.6.1.2 Kaplan-Meier Analysis

Kaplan-Meier (KM) analysis will be used to evaluate time to oxygen therapy initiation from the fibrosing ILD diagnosis date among patients without baseline oxygen therapy use. When KM analysis is conducted, results will include censored-adjusted percentage of patients who have the event of interest at pre-specified time periods of interest (e.g., 6 month, 9 months, 12 months). In addition, the median (and 25th and 75th percentile) time to event and the 95% confidence interval (CI) around the median (and 25th and 75th percentile) will be reported. Censoring will occur at the first of the following: disenrollment from the health plan, end of the study period, or death.

Graphs of the cumulative incidence functions (i.e., $1-S(t)$ where $S(t)$ is the survival function) will be presented along with the cumulative percentage of patients with oxygen therapy initiation following the fibrosing ILD diagnosis date. Methods may account for competing events (e.g., death as competing event for oxygen therapy initiation).

[figure not shown]

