7.3 VARIABLES

Variables related to the study period will be defined as follows:

Aim 1

- **Fibrosing ILD diagnosis date**—The first ILD diagnosis date for patients with ≥ 2 fibrosing ILD diagnoses on different dates and within 365 days. The fibrosing ILD diagnosis date is the first day of follow-up observation time for Aim 1.
- **Pre-ILD baseline period**—The 12-month period prior to the fibrosing ILD diagnosis date.
- **Aim 1 follow-up period**—The variable period starting on the fibrosing ILD diagnosis date and continuing until the earliest of the following: disenrollment from the health plan, death, or end of the study period. The Aim 1 follow-up period will be used to assess Aim 1 outcomes.
 - **All-cause mortality**—Death will be used as a censoring event and is further defined in Section 7.3.3.1.

Aim 2

- **Index date**—For the oxygen therapy cohort, the first date following the fibrosing ILD diagnosis date with a claim with diagnosis for oxygen therapy; for the no oxygen therapy cohort, a date within the same continuous enrollment period as the fibrosing ILD diagnosis date that is similar to the matched oxygen therapy patient in time from fibrosing ILD to index date. The index date is the first day of follow-up observation time for Aim 2 and Further Aim.
- **Pre-index baseline period**—The 12-month period prior to the index date.
- **Aim 2 follow-up period**—The variable period starting on the index date until the earliest of the following: disenrollment from the health plan, death, or the end of the study period. Matched pairs will be given the same duration of follow-up. The Aim 2 follow-up period will be used to assess Aim 2 and Further Aim outcomes.
 - **All-cause mortality**—Death will be used as a censoring event and is further defined in Section 7.3.3.1.

An overview of the analytic study variables and the study periods for which each analytic variable will be reported is provided in Table 1. Additional variable information is provided in Sections 7.3.1 to 7.3.4.

Table 1. Analytic Variables by Data Source and Time Period

Characteristic	Data source		Aim 1 time period		Aim 2 time period	
	Claims*	EHR	Pre-ILD baseline	Follow-up	Pre-index baseline	Follow-up
Aim 1 outcomes						
Oxygen therapy (time to initiation, sustained oxygen therapy use)		X		X	X	
Aim 2 outcomes						
Disease progression	X	X				X
All-cause mortality	X					X
Hypoxemia	X	X	X		X	X
Acute exacerbations	X	X				X
Patient characteristics†						
Index year	X		X		X	

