7.3.3 Aim 2 Outcomes

7.3.3.1 Primary Outcomes

All primary outcomes will be measured in the Aim 2 and Further Aim follow-up period, unless specified otherwise.

- **Time to disease progression**—Pulmonary function test (PFT) results will be captured as available in the database in the pre-ILD baseline, pre-index baseline, and Aim 2 follow-up periods among the subset of patients who have EHR data during the same

time of ILD diagnosis and oxygen therapy. All valid result values will be captured. Values closest to the fibrosing ILD diagnosis date will be reported for the pre-ILD baseline period; values closest to the index date will be reported for the pre-index baseline period; the latest values prior to the end of follow-up will be reported for the Aim 2 follow-up period. PFT tests may potentially include forced expiratory volume in 1 second (FEV₁), forced vital capacity (FVC), FEV₁/FVC ratio, lung volumes, and diffusing capacity for carbon monoxide (DLCO), as available.

Among patients or matched pairs with FVC results in the pre-index and follow-up periods, disease progression will be defined as a 10% relative change between the pre-index value and the follow-up value. Time to disease progression will be reported. Additionally, time in days from pre-index FVC result to the index date and from index date to follow-up FVC result will be reported.

- **Time to all-cause mortality**—We will assign the date of death as the 15th day in the month of death. Time to all-cause mortality will be calculated as time between index date and mortality date.

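### Aim 1 censors death and labels 1−S(t) cumulative incidence, so Kaplan-Meier uptake of oxygen is at or above the competing-risk estimate: probably by little at 6–12 months, by an unknown amount later

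*Combined protocol and SAP*

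**What the plan says.** Section 7.6.1.2 (repeated in the Abstract under Data analysis) uses Kaplan-Meier for the time from fibrosing ILD diagnosis to first oxygen, among patients without baseline oxygen. The censoring rule is: "Censoring will occur at the first of the following: disenrollment from the health plan, end of the study period, or death". From this analysis it takes:

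- the "censored-adjusted percentage of patients who have the event of interest at pre-specified time periods of interest (e.g., 6 month, 9 months, 12 months");
- "the median (and 25th and 75th percentile) time to event", with confidence intervals;
- "Graphs of the cumulative incidence functions", which it defines as 1−S(t) with S(t) the survival function.

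Section 7.3 agrees with the censoring rule for Aim 1 follow-up: "Death will be used as a censoring event". The one counterweight is a closing sentence in Section 7.6.1.2: "Methods may account for competing events (e.g., death as competing event for oxygen therapy initiation"). The readable text names no estimator, no condition for using one and no primary estimate. The limitations (Section 7.8) do not mention the issue, and Annex 1 lists no stand-alone document that could settle it.

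**The concern.** Death before oxygen precludes initiation. Censoring these patients treats them as if they could still start oxygen later, at the rate seen in patients still under observation. The result, 1−S(t), is a death-censored net quantity and not the proportion who start oxygen before dying, which is what a cumulative incidence function describes.

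The incidence of oxygen use and the time to first oxygen are Aim 1 objectives (Section 6), so the label bears on a main result. Results are also split by IPF and non-IPF. If mortality before oxygen differs between these groups, the gap differs too, and so would the comparison of absolute uptake. Finally, an optional method leaves the choice of estimator open until after the data have been seen.

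**Working it through.** **No figure to reproduce.** The plan states no expected incidence, death rate or event count for this analysis.

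**Direction.** At an oxygen event time t with dN starts among R patients at risk:

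- the step in 1−KM is S_KM(t−) × dN/R;
- the Aalen-Johansen step is S_all(t−) × dN/R, where S_all also falls at each death.

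Since S_all ≤ S_KM, 1−KM is at or above Aalen-Johansen at every time, and any quantile that KM reaches comes no later. The two are equal as long as no death has occurred. A check on 300 simulated data sets of 300 patients each found no violation beyond rounding error.

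**Size: inputs.**

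- *Initiation at 12 months:* 214,725 / 1,179,017 = 18.2% (Section 7.5, Table 3). This is a crude feasibility ratio, not limited to oxygen-naive patients or to the study's selection criteria. It serves only as an anchor and is read here as a net risk. The hazard is l = −ln(1 − 0.182) = 0.201 per year.
- *Death hazard before oxygen, m:* 0.02 to 0.30 per year. This is an assumption; the documents give no value.
- *Death-free time, d:* 0.25 years. This is also an assumption. Section 7.2.2 requires a second diagnosis on a different date within 365 days, so no included patient can die before that date.
- *Maximum follow-up:* 01 October 2016 to 30 June 2022 = 5.75 years (Section 7.1), longer if the study period is extended.

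**Formulas (constant hazards).**

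- 1−KM(t) = 1 − exp(−l·t)
- CIF(t) = 1 − exp(−l·d) + exp(−l·d) × [l/(l+m)] × [1 − exp(−(l+m)(t−d))], for t ≥ d

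**Worked case, m = 0.20.** exp(−l·d) = 0.951 and l/(l+m) = 0.501.

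- 1 year: CIF = 0.049 + 0.951 × 0.501 × 0.260 = 17.3%, against 18.2% by KM.
- 3 years: CIF = 0.049 + 0.951 × 0.501 × 0.668 = 36.8%, against 45.3% by KM.

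| m per year | Excess at 6 mo (points) | 9 mo | 12 mo | 3 y | Median, competing-risk (KM 3.45 y) |
|---|---|---|---|---|---|
| 0.02 | 0.0 | 0.0 | 0.1 | 1.0 | about 3.6 y |
| 0.05 | 0.0 | 0.1 | 0.2 | 2.4 | 3.82 y |
| 0.10 | 0.1 | 0.2 | 0.5 | 4.6 | 4.36 y |
| 0.20 | 0.1 | 0.4 | 0.9 | 8.5 | 7.53 y (beyond 5.75 y) |
| 0.30 | 0.2 | 0.6 | 1.4 | 11.9 | never |

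**Sensitivity to the assumptions.**

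- With d = 0, the excess is 0.2–2.4 points at 12 months and 1.2–14.1 at 3 years.
- With d = 1 year, the extreme that the 365-day window allows, it is zero through 12 months and 0.5–6.3 points at 3 years.

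**Which quantiles KM could report within 5.75 years.** A KM median needs 12-month initiation above 1 − exp(−ln 2/5.75) = 11.4%. A KM 75th percentile needs more than 1 − exp(−ln 4/5.75) = 21.4%. At 18.2% the KM 75th percentile would fall at ln 4/0.201 = 6.90 years, so none would be reported. At an assumed 30% with d = 0.25, the KM 75th percentile is 3.89 years, against 6.09 years at m = 0.10 and never at m = 0.20 or more.

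**The case against.** **The plan has not overlooked the problem.** It names death as a competing event for this very outcome. That is fair: the gap is in commitment and labelling, not awareness. But the committed default is still the death-censored curve under the wrong name.

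**The gap is small where the plan looks.** The only named time points are 6, 9 and 12 months. This stands, and a reader should not infer a material overstatement there. The relevant hazard is death before any oxygen code, and Section 7.3.1.1 counts a single code as use. Patients who deteriorate may therefore record oxygen before they die, which makes low hazards plausible. The plan also commits to full curves and quartiles, however, and these extend beyond 12 months.

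**Incidence need not mean cumulative incidence.** Section 6 does not define it, and a person-time rate properly stops at death. This stands for such a rate, but not for outputs that Section 7.6.1.2 itself calls cumulative incidence functions.

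**Three stronger readings are tempting but unsupported.**

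- *Every Aim 1 percentage is too high.* The direction holds only for the KM outputs. A crude proportion can fall below the competing-risk value: in one simulated cohort of 40,000 with assumed disenrollment, the 12-month figures were 18.0% by KM, 17.1% by Aalen-Johansen and 14.7% crude. Section 7.6.1.2 does not say how the "cumulative percentage of patients with oxygen therapy initiation" is calculated.
- *KM gives the risk if nobody died.* That requires death and initiation to be independent. Both may track disease severity, and the documents give no ground for assuming independence.
- *The Cox model is wrong too.* Censoring death in Section 7.6.1.3 gives cause-specific hazard ratios, which suit a question about factors associated with initiation.

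**Conclusion.** The concern holds for the KM curve, the time-point percentages and the quantiles. The direction is algebraic and needs no assumption about rates. The size cannot be taken from the documents. The ranges above rest on constant hazards, a crude 18.2% anchor, an assumed death hazard and an assumed death-free interval. On that basis the excess is likely small at 6–12 months, and zero at any time point before which no one can die. It may be material for the later curve, the median and the 75th percentile. The change is worth making because it concerns a stated objective and costs little. Nothing in the documents shows that the reported 12-month figures would be seriously wrong.

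**What to change.** In Section 7.6.1.2 and the Abstract:

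- Change 'may' to 'will' in the competing-events sentence.
- Prespecify the Aalen-Johansen cumulative incidence, with death before oxygen as the competing event and only disenrollment and study end censored. Use it for the graphs, time-point percentages and quantiles, overall and by IPF/non-IPF.
- Report a quantile as not reached where the curve does not get there.
- Show 1−S(t), if at all, as a supplementary death-censored quantity that is not called cumulative incidence.
- State that the estimate describes patients who survived to a second qualifying diagnosis. Aalen-Johansen does not remove that selection.

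In Section 7.3, make death a competing event instead of a censoring event for this outcome. Keep the Cox model in Section 7.6.1.3 and describe its hazard ratios as cause-specific.

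Optional refinement: Section 7.3.3.1 says "We will assign the date of death as the 15th day in the month of death". A short rule could set the order of death, disenrollment and oxygen claims within the month of death. How much this matters depends on when enrollment ends relative to death, which the documents do not state.

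Cost: wording changes and a standard estimator in the SAS software already named, with no new data. The downside is that reported uptake will be slightly to moderately lower, and some quantiles may not be reached.
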